10 STATISTICAL ANALYSIS

10.1 General Considerations

The Schedule of Assessments is provided in the clinical study protocol (CSP) Table 3-1. The precision standards for reporting safety and efficacy variables are provided in an internal Biometrics document that specifies the programming rules including the precision for derived variables.

All individual subject data for subjects who were enrolled in a parent study and who received at least 1 dose of TEZ/IVA in either parent study or in Study 116 will be presented in individual subject data listings.

Continuous variables will be summarized using the following descriptive summary statistics: the number of subjects (n), mean, standard deviation (SD), median, minimum value (min), and maximum value (max).

Categorical variables will be summarized using counts and percentages. Percentages will be presented to 1 decimal place.

Day 1, unless specified otherwise, will be defined as the day of the first dose of TEZ/IVA, in the Study 116 Part A.

Baseline value for safety analysis will be defined as the most recent non-missing measurement (scheduled or unscheduled) collected before the first dose of TEZ/IVA, whether the first dose was taken in the parent study or in Study 116 Part A. For ECGs, the baseline value will be defined as the last non-missing measurement (scheduled or unscheduled) before the first dose of TEZ/IVA or the average of measurements (triplicate) before the first dose of TEZ/IVA, whether the first dose was taken in the parent study or in Study 116 Part A.

Baseline value for efficacy analysis will be defined as the same as baseline of the parent study.

Change (absolute change) from baseline will be calculated as $\frac{\text{Post-baseline value} - \text{Baseline value}}$.

Relative change from baseline will be calculated and expressed in percentage as $\frac{100\% \times (\text{Post-baseline value} - \text{Baseline value})}{\text{Baseline value}}$.

The data from Study 116 will be integrated with data from the parent studies for the purpose of providing robust safety and efficacy analyses.

Unscheduled visits: Unscheduled visit measurements will be included in analysis as follows:

- In scheduled visit windows per specified visit windowing rules.
- In the derivation of baseline measurements.
- In the derivation of maximum/minimum values and maximum/minimum change from baseline values for safety analyses.
- In individual subject data listings as appropriate.

Visit windowing rules: The analysis visit windows for protocol-defined visits are provided in [Appendix A](#).

Incomplete/Missing data will not be imputed, unless otherwise specified.

Outliers: No formal statistical analyses will be performed to detect or remedy the presence of statistical outliers, unless otherwise specified.

Multiplicity: No multiplicity adjustment will be performed.

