9.1.1 Treatment Period

Treatment Period assessments are listed in [Table 3-1](#).

The Day 1 Visit of Study 116 will be on the **same day** as the last scheduled visit of the parent study; this will occur at the Week 24 Visit for subjects from Study 113B and at the Week 8 Visit for subjects from Study 115. Subjects will NOT have to repeat any Study 116 Day 1 Visit assessments that were specified to be performed at the last scheduled visit in the parent study.

Subjects who were enrolled in Study 116, but had Day 1 study drug administration procedures delayed (e.g., due to an AE), will repeat the safety, LCI (if applicable), [REDACTED] assessments that were specified to be performed at the Day 1 Visit before receiving their first dose of study drug.

For subjects at Study 116 sites that have NOT been activated by the time the subject has completed the last scheduled visit in the parent study, the Day 1 Visit of Study 116 will NOT coincide with the last scheduled visit of the parent study. Subjects at these sites with delayed activation will have to repeat any Study 116 Day 1 assessments that were specified to be performed at the last scheduled visit in the parent study.

All subjects will have study visits on Day 1 and at Weeks 12, 24, 36, 48, 60, 72, 84, and 96.

Study Visits on Day 15 and Week 4 are only required for subjects from Study 115.

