12.3.1 General Considerations

The precision standards for reporting safety and efficacy variables are provided in an internal Biometrics document that specifies the programming rules including the precision for derived variables.

All individual subject data for subjects who were enrolled in a parent study and who received at least 1 dose of TEZ/IVA in either parent study or in Study 116 will be presented in individual subject data listings.

Continuous variables will be summarized using the following descriptive summary statistics: the number of subjects (n), mean, SD, SE, median, minimum value (min), and maximum value (max).

Categorical variables will be summarized using counts and percentages.

Day 1, unless specified otherwise, will be defined as the day of the first dose of TEZ/IVA, whether the first dose was taken in the parent study or in Study 116.

Baseline value, unless specified otherwise, will be defined as the most recent non-missing measurement (scheduled or unscheduled) collected before the first dose of TEZ/IVA, whether the first dose was taken in the parent study or in Study 116. For ECGs, the baseline value will be defined as the average of the last non-missing pretreatment measurements (scheduled or

unscheduled) before the first dose of TEZ/IVA or the average of measurements (triplicate) before the first dose of TEZ/IVA, whether the first dose was taken in the parent study or in Study 116.

Change (absolute change) from baseline will be calculated as Post-baseline value – Baseline value.

Relative change from baseline will be calculated and expressed in percentage as 100% × (Post-baseline value – Baseline value)/Baseline value.

The data from Study 116 will be integrated with data from the parent studies for the purpose of providing robust safety and efficacy analyses.

Unscheduled visits: Unscheduled visit measurements will be included in analysis as follows:

- In scheduled visit windows per specified visit windowing rules.
- In the derivation of baseline/last on-treatment measurements.
- In the derivation of maximum/minimum on-treatment values and maximum/minimum change from baseline values for safety analyses.
- In individual subject data listings as appropriate.

Visit windowing rules: The analysis visit windows for protocol-defined visits will be provided in the SAP.

Incomplete/missing data will not be imputed, unless specified otherwise.

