8 ANALYSIS SETS

The following analysis sets are defined for Study 116 Part A: All Subjects Set, Safety Set, Full Analysis Set, 113B/116 Full Analysis Set, 115/116 Full Analysis Set, and 113B/116 LCI Full Analysis Set.

Enrolled subjects are those who signed a consent/assent form and had an enrollment date in the CRF for Part A.

All Subjects Set

The **All Subjects Set** will be defined as all subjects who were enrolled in Study 116 Part A or received at least 1 dose of TEZ/IVA in Study 116 Part A. This analysis set will be used for all individual subject data listings and the disposition summary table, unless specified otherwise.

Full Analysis Set (FAS)

The **Full Analysis Set (FAS)** will be defined as all subjects who were enrolled in Study 116 Part A, who received at least 1 dose of TEZ/IVA in Study 116 Part A and have an eligible genotype. The FAS will be used for efficacy analyses, unless otherwise specified.

115/116 Full Analysis Set (FAS), 113B/116 FAS and 113B LCI/116 FAS

The 115/116 FAS will be defined as the subset of FAS who were enrolled in parent Study 115. The 113B/116 FAS will be defined as the subset of FAS who were enrolled in parent Study 113B. The 113B/116 LCI FAS will be defined as the subset of Study 113B subjects who participated in the LCI sub-study in Study 113B.

Safety Set

The **Safety Set** will be defined as all subjects who are enrolled in study 116 Part A and who received at least 1 dose of TEZ/IVA in Study 116 Part A. The Safety Set will be used for all safety analyses, unless otherwise specified.

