10.4.2.2 Absolute Change from Baseline in Sweat Chloride

The absolute change from baseline in sweat chloride at Weeks 24, 48 and 96 will be analyzed using a MMRM as specified above.

The analysis will be performed using a restricted maximum likelihood (REML)-based mixed-effect model for repeated measures (MMRM) for the subjects in the 115/116 FAS and the 113B/116 FAS separately.

For 115/116 FAS , the model will include absolute change from baseline in sweat chloride measurements at Weeks 24, 48 and 96 as the dependent variable, and visit (as a class variable), mutation group (F/F and F/RF) as a fixed effects, and baseline sweat chloride (continuous) value and baseline LCI2.5 as covariates, and subject as a random effect.

For 113B/116 FAS, the model will include absolute change from baseline in sweat chloride measurements at Weeks 24, 48 and 96 as the dependent variable, and visit (as a class variable) as a fixed effect, baseline sweat chloride (continuous) value as covariate, and subject as a random effect.

For subjects from Study 115, only those who were randomized to TEZ/IVA treatment group will be included in the MMRM model.

For each visit, the LS mean, standard error (SE), and associated 95% CI, will be provided. The LS mean and associated 95% CI at each visit will also be plotted.

Additionally, the raw values and change from baseline values of sweat chloride measurements will be summarized for subjects in the 113B/116 FAS , for subjects in the 115/116 FAS who were randomized to TEZ/IVA (in Study 115), and for the 115/116 FAS overall at weeks 24, 48 and 96.

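### The SAP's parent-study baseline for efficacy puts about 8 pre-drug weeks into the descriptive change scores of Study 115 subjects not randomised to TEZ/IVA

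*SAP*

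**What the plan says.** Protocol 12.3.1 sets one default baseline for all analyses: "Baseline value, unless specified otherwise, will be defined as the most recent non-missing measurement (scheduled or unscheduled) collected before the first dose of TEZ/IVA". It applies wherever that first dose was taken, in the parent study or in Study 116.

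SAP 10.1 splits this rule in two. For safety it repeats the protocol: "Baseline value for safety analysis will be defined as the most recent non-missing measurement (scheduled or unscheduled) collected before the first dose of TEZ/IVA". For efficacy it says: "Baseline value for efficacy analysis will be defined as the same as baseline of the parent study". No reason is given and no subgroup is exempted. The visit-window table in SAP Appendix A refers every efficacy endpoint back to Section 10.1 for its baseline, so this sentence governs all four secondary endpoints.

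On who is analysed, SAP 8 states: "The 115/116 FAS will be defined as the subset of FAS who were enrolled in parent Study 115". Parent-study arm plays no part in that definition. The mixed models for Study 115 are limited to subjects randomised to TEZ/IVA (Protocol 12.3.3.2; SAP 10.4.2.1 to 10.4.2.4). The descriptive summaries of raw values and change are not. They cover the TEZ/IVA-randomised subjects and then the whole set, for example for sweat chloride "and for the 115/116 FAS overall at weeks 24, 48 and 96". LCI2.5, CFQ-R and BMI have the same pair of summaries.

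**The concern.** For a subject given TEZ/IVA from the start of the parent study, the two rules should pick the same value. They part for a Study 115 subject in the other arm. The SAP provides for such subjects: 10.2.2 allows for a first TEZ/IVA dose taken in Study 116, and 10.3 limits the pooled parent-study adverse events to those who received TEZ/IVA.

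For these subjects the SAP baseline precedes the drug by the length of Study 115. Change from that baseline mixes a pre-drug period with the response to TEZ/IVA. The early visits suffer most, and that is where a reader would look for onset in newly treated children. For BMI the pre-drug weeks also include growth, which Protocol 9.3.3 says must be allowed for when nutritional change is assessed. The overall row then pools two groups for whom change from baseline means different things.

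A related gap is that SAP 10.2.2 reports sweat chloride, CFQ-R and LCI2.5 at a treatment baseline, and a note to Appendix A uses the same term for weight in the threshold analysis. SAP 10.1 does not define it. If it means the last value before TEZ/IVA, the baseline table and the change tables start from different values for the same subjects.

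**Working it through.** The plan states no figure to reproduce. Two short calculations give the size.

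**1. Share of the change interval that precedes TEZ/IVA**

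Inputs:
- Study 116 Day 1 normally falls "at the Week 8 Visit for subjects from Study 115" (Protocol 9.1.1), so about 8 weeks separate the parent baseline from the first TEZ/IVA dose.
- At sites activated late, "the Day 1 Visit of Study 116 will NOT coincide with the last scheduled visit of the parent study", and Day 1 dosing may also be delayed. The gap is then longer, so 8 weeks is roughly a minimum.
- Post-baseline values come from Study 116, because the efficacy period starts at its first dose (SAP 9.1).
- Nominal visit times are used. Day 15 is (15 − 1)/7 = 2 weeks after the first dose.

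Formula: share = 8 / (8 + weeks since the first Study 116 dose).

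| Study 116 visit | Weeks since parent baseline | Share before TEZ/IVA | Endpoints summarised at this visit |
|---|---|---|---|
| Day 15 | 8 + 2 = 10 | 8/10 = 80.0% | LCI2.5, CFQ-R, BMI |
| Week 4 | 8 + 4 = 12 | 8/12 = 66.7% | LCI2.5, CFQ-R, BMI |
| Week 24 | 8 + 24 = 32 | 8/32 = 25.0% | all four |
| Week 48 | 8 + 48 = 56 | 8/56 = 14.3% | all four |
| Week 72 | 8 + 72 = 80 | 8/80 = 10.0% | LCI2.5, CFQ-R, BMI |
| Week 96 | 8 + 96 = 104 | 8/104 = 7.7% | all four |

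These are shares of elapsed time. They do not say what fraction of the measured change arose before the drug. Sweat chloride is first summarised at Week 24, so the two largest shares do not apply to it.

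**2. Shift in the overall Study 115 mean**

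Let c be the proportion of the 115/116 FAS not randomised to TEZ/IVA, and m their mean change over the pre-drug weeks. The overall mean change under the SAP rule differs from that under the protocol rule by c × m.

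Neither quantity is in the documents. About 65 Study 115 subjects were potentially eligible (SAP 7.2). Assumed values of c:
- 13 of 65: c = 0.20
- 22 of 65: c = 0.34
- 32 of 65: c = 0.49

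Each unit of m therefore moves the overall mean by 0.20 to 0.49 units. As an illustration only, m = 3 CFQ-R points would give 0.20 × 3 = 0.6 to 0.49 × 3 = 1.5 points, and m = 0.2 kg/m² would give 0.20 × 0.2 = 0.04 to 0.49 × 0.2 = 0.10 kg/m². If m is near zero, so is the shift.

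**After the change.** With the pre-TEZ/IVA baseline, the pre-drug interval for these subjects falls from about 8 weeks to about zero.

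**The case against.** The strongest reply is that the SAP is within its rights. The protocol's baseline rule applies unless something else is specified, details of method are left to the SAP, and efficacy methods are meant to resemble those of the parent studies (Protocol 12.3). A reader might infer that the SAP contradicts the protocol. It does not: it makes a permitted departure without explaining it.

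The reach is also narrow. A reader might infer that the modelled efficacy results are biased. The models exclude these subjects, so no least-squares mean, standard error, confidence interval or plot of them changes. The unaffected row for TEZ/IVA-randomised subjects already stands beside the overall row. Efficacy is a secondary objective, and the safety baseline follows the protocol.

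Two further inferences fail. One is that the overall rows are the only efficacy output containing these subjects. Raw-value summaries and individual listings also cover them, and the public SAP has gaps where further efficacy sections may stand. The other is that BMI is given two baselines. The Appendix A note concerns weight in a safety threshold analysis, and BMI is not in that analysis.

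Finally, re-baselining does not make the overall row homogeneous. At Study 116 Week 24 the parent TEZ/IVA arm has had about 8 + 24 = 32 weeks of drug and the other arm 24.

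All of this stands, and it limits the point. It does not remove it: for these subjects the stated rule still yields a change that does not isolate time on TEZ/IVA, and the SAP does not warn the reader.

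**Conclusion.** The point holds for one set of outputs: the descriptive change from baseline in the overall 115/116 FAS for LCI2.5, sweat chloride, CFQ-R and BMI. For Study 115 subjects not randomised to TEZ/IVA, at least about 8 weeks of that change precede the drug. This dominates the interval at the earliest visits and is a small part of it at Week 96.

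The effect on the overall means cannot be sized from the documents and may be small.

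The conclusion rests on three assumptions. Subjects not randomised to TEZ/IVA in Study 115 took their first dose in Study 116; the SAP implies this, but neither document describes what they received before. The parent-study baseline is the last value before parent-study dosing, so the two rules agree for TEZ/IVA-randomised subjects. All Study 113B subjects took TEZ/IVA from the start of that study.

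**What to change.** 1. In SAP 10.1, define the efficacy baseline as the last non-missing value before the first TEZ/IVA dose in either study, as Protocol 12.3.1 does.
2. Define treatment baseline in the same way in SAP 10.1, so that its uses in SAP 10.2.2 and Appendix A are unambiguous.
3. In the 115/116 descriptive tables, add a row for subjects not randomised to TEZ/IVA beside the existing TEZ/IVA-randomised and overall rows. This is needed even after re-baselining, because time on the drug still differs between the arms.

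The cost is a changed baseline flag for these subjects and one extra row per table. No new data are needed: CFQ-R, height and weight, multiple-breath washout and sweat chloride are all scheduled at Day 1 (Protocol Table 3-1), or carry over from the last parent-study visit when the two coincide.

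If the sponsor prefers the parent-study baseline, the SAP should say why and show these subjects separately under both baselines.

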10.2 Background Characteristics

10.2.1 Subject Disposition

A summary table of subjects' disposition will be presented for the All Subjects Set for the following categories:

- All Subjects Set
- Safety Set
- Full Analysis Set

The number and percentage of subjects in each of the following disposition categories will be presented based on the Safety Set:

- Completed study drug treatment in Part A
- Prematurely discontinued the treatment in Part A and the reason for discontinuation
- Completed Safety Follow-up in Part A
- Did not complete Safety Follow-up in Part A and the reason for not completing

A listing will be provided for subjects who discontinued treatment during Study 116 Part A or who discontinued Study 116 Part A, with reasons for discontinuation.

10.2.2 Demographics and Baseline Characteristics

Demographics and treatment baseline characteristics will be summarized based on the FAS, and will be presented by 115/116 FAS, and 113B/116 FAS, and overall. Note: all efficacy analysis will be presented by parent study, hence this may be informative.

Demographic data will include the following:

- Age (in years)
- Sex (female and male)
- Ethnicity (Hispanic or Latino, not Hispanic or Latino, and not collected per local regulations)
- Race (White, Black or African American, Asian, American Indian or Alaska Native, Native Hawaiian or Other Pacific Islander, and Other)
- Geographic region (North America, Europe, and Australia)
- *CFTR* genotype group (*F508del/F508del*; *F508del/Residual Function*)

Baseline characteristics will include the following:

- Weight (kg)
- Weight group (<30 kg, 30-40kg, and ≥40 kg)

■ [REDACTED]

- Height (cm)

■ [REDACTED]

- BMI (kg/m²)

■ [REDACTED]

Disease characteristics will include the following:

■ [REDACTED]

■ [REDACTED]

- Sweat chloride at treatment baseline

- CFQ-R respiratory domain score at treatment baseline
- LCI_{2.5} at treatment baseline (Study 115 subjects and 113B LCI sub study subjects only)
- Prior use of dornase alfa (Yes, No)
- Prior use of azithromycin (Yes, No)
- Prior use of inhaled antibiotic (Yes, No)
- Prior use of any bronchodilator (Yes, No)
- Prior use of any inhaled bronchodilator (Yes, No)
- Prior use of any inhaled hypertonic saline (Yes, No)
- Prior use of any inhaled corticosteroids (Yes, No)
- Infection with *Pseudomonas aeruginosa* within 2 years prior to parent study screening (Positive, Negative)

Prior medication use refers to medication taken before the first dose date of TEZ/IVA regimen in either the parent study (if the subject received the first dose of TEZ/IVA regimen in the parent study) or Study 116 Part A (if the subject received the first dose of TEZ/IVA regimen in Study 116 Part A).

10.2.3 Medical History

Medical history (referenced to the start of parent study) will be coded by using the Medical Dictionary for Regulatory Activities (MedDRA) system organ class (SOC) and preferred term (PT), and will be summarized based on the FAS and displayed by 115/116 FAS, and 113B/116 FAS, and overall.

10.2.4 Prior and Concomitant Medications

Medications will be coded using the World Health Organization Drug Dictionary (WHODD) and categorized as follows:

- **Prior medication:** any medication that started before the first dose date of study drug
- **Concomitant medication:** medication continued or newly received during the TE period. A given medication may be classified as prior, concomitant, or both prior and concomitant. If a medication has a completely missing or partially missing start/stop date and it cannot be determined whether it was taken before the first dose date or concomitantly, it will be classified as prior and concomitant.
- **Post-treatment medication:** medication continued or newly received after the TE period.

Prior medications and concomitant medications will be summarized descriptively by: 1) preferred name (PN); and 2) anatomic class (ATC) level 1, ATC level 2, and PN, based on the 116A FAS and will be presented by 115/116 FAS, and 113B/116 FAS, and overall. Details for imputing missing or partial start and/or stop dates of medication are described in [Appendix D](#).

10.2.5 Study Drug Exposure

Duration of study drug exposure (in days) will be calculated as: last dose date – first dose date + 1 day, regardless of study drug interruption. The first and last dose dates of Study 116 Part A will be used for the calculation.

Study drug exposure will be summarized descriptively by the number of subjects (n), mean, SD, median, min, and max based on the 116A Safety Set. It will also be summarized into the following categories: >0 to ≤12 weeks, >12 to ≤24 weeks, >24 to ≤36 weeks, >36 to ≤48 weeks, >48 to ≤60 weeks, >60 to ≤72 weeks, >72 to ≤84 weeks, >84 to ≤96 weeks, >96 weeks, using counts and percentages.

Additionally, the total study drug exposure, defined as the sum of the study drug exposure across all subjects (in patient-years), will be provided.

Exposure summaries will be based on the Safety Set.

10.2.6 Study Drug Compliance

The study drug compliance will be calculated based on the study exposure (in days) as well as based on the number of tablets taken; summary of both calculations will be provided.

Study drug compliance based on study drug exposure will be calculated as: $100 \times [1 - (\text{total number of days of any study drug interruption}) / (\text{duration of study drug exposure in days})]$.

Study drug compliance based on the number of tablets taken will be calculated as: $100 \times [(\text{total number of tablets dispensed}) - (\text{total number of tablets returned})] / (\text{total number of tablets planned to be taken per day} \times \text{duration of study drug exposure in days})$. The maximum percentage of tablets taken will be 100%.

Both Study drug compliance variables will be summarized descriptively by the n, mean, SD, median, minimum, and maximum. They will also be summarized in categories: <80% and ≥80% using frequency tables.

Study drug compliance summaries will be based on the FAS, and will be presented by 115-116 FAS, and 113B-116 FAS, and overall.

